We will examine the role of mother-child attachment in the development of early psychopathology in children with and without prenatal adversity, defined by birth weight (corrected for gestational age). We will also focus on early manifestations of psychopathology in order to study possible factors that might modify the risk of psychopathology before these pathologies become entrenched, and associated with disability later on. Such studies are consistent with the increased capacity for neuroplasticity over early childhood. This is a major advantage of the prospective, longitudinal approach of the MAVAN study.

An additional feature of the MAVAN studies is that of understanding the factors that influence the quality of mother – child interactions. Thus, we examine the quality of the maternal environment using measures that are known as the best predictors of individual differences in maternal care and infant attachment. The best environmental measures are those of ‘marital’ support and stress. Since both factors appear to operate through maternal mental health, we also include measures of maternal well-being. While we focus on those measures that are specific to the 72-month protocol, measures of mother – child interaction, maternal environment and maternal well being have been included in MAVAN since the prepartum period.

Hypothesis 1: The relation between birth weight and measures of childhood mental health will be moderated by the quality of post-natal maternal care. We will focus on two outcomes measures, the Connors questionnaire and the DOMINIC/QUE questionnaire.

Hypothesis 2: The quality of postnatal mother – infant interaction will be influenced by the quality of the maternal environment and maternal mental well being.

Measures

We focus our description on measures that are new to the MAVAN study. This list of measures is complete, and we note where measures have been previously approved. Also, in accordance with the comments on the previous submission, we emphasize new measures.

Seventy-two month interview: Home visit (150 minutes)

Mothers

Interview: Questionnaire on Maternal Well-Being (30 minutes)

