This questionnaire has already been accepted by the Douglas Hospital Ethic Board with the original submission of the MAVAN project. This program of research examines the impact of maternal adversity on child development. Therefore, it is critical that we regularly monitor the level of maternal adversity. An extensive maternal interview protocol was administered at 6, 12, 24, 36, 48 and 60 months post-partum. At 72 months, we plan to administer the same version as used at 24 and 60 months.

The following questionnaires have already been accepted by the Douglas Hospital Ethic Board for different time points including in the initial submission: **Housing conditions** (10 minutes); **Health** of families (5 minutes); **Sleep patterns** (5 minutes) of children; the **Strength and Difficulties Questionnaire** (5 minutes) for screening psychopathology in children; and the **Beck Depression Inventory** (5 minutes) for assessing depressive symptoms in mothers.

Questionnaires (45 minutes)

Family Functioning (Family Assessment Device):

This questionnaire assesses family functioning on each dimension of the McMaster Model of Family Functioning (MMFF) according to individual family member's perception of their family's functioning. In addition to the six subscales of the MMFF (Problem solving, communication, roles, affective responsiveness, affective involvement, behaviour control) the FAD includes a General Functioning scale that measures the overall level of the family's functioning. Sixty statements, geared to an eighth-grade reading level, describe various aspects of family functioning. Each member of the family over the age of 12 completes the pen-and-paper questionnaire by rating how well the statement describes his or her family. There are four choices (strongly agree, agree, disagree, strongly disagree) per item for each dimension. Dimension items are purposely not listed in consecutive order. Each item matches only one dimension and may describe healthy or unhealthy functioning. The FAD takes approximately 20 minutes to complete.

Conner's questionnaire:

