The measure has been previously approved for use in the MAVAN study. Developed by C. [name]., the Conners' Rating Scales-Revised (CRS-R) are paper and pencil screening questionnaires designed to be completed by parents and teachers to assist in evaluating children (3-17 years) for **attention-deficit/hyperactivity disorder** (ADHD). The parents' short version contains 27 items and the teachers' short version has 28. The teacher version is similar but lacks the psychosomatic scale contained on the parent version. The Conner's is validated and the standard for informant-administered ADHD assessment both in clinical and research settings.

Family History Screen (FHS)

The FHS, a validated brief family psychiatric history instrument (Weissman et al, 2000) is administered to a parent, who reports on their child as well as on the proband's immediate biological relatives (biological parents, siblings). It takes 5 to 20 minutes to administer, depending on the size of the family and the presence of family illness. Information on 15 lifetime psychiatric disorders and suicide attempts is obtained. The

FHS begins with general questions about psychopathological features, treatment, and impairment, followed by more specific questions about psychopathological features during the course of the entire lifetime of all family members. If the informant answers affirmatively to any question, the interviewer determines specifically which family members had the symptom and records the name and identifying number. Probes are included for inquiring about family members and for helping the informant recall which relatives are involved. Periodically, the interviewer is instructed to remind the informant by naming the relatives. There is at least 1 question for each diagnosis (for major depressive disorder [MDD], there are 3; for mania, panic, conduct, and antisocial personality disorders, 2) that corresponds to the core symptom(s) of the disorder. Understanding the background of families is key to understanding the role of familial transmission.

Actiwatch

This measure has already been accepted by the Douglas Hospital Ethic Board for different time points included in the initial submission.

Children

THE DOMINIC=R QUESTIONNAIRE: (20 minutes)

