The Dominic questionnaire (Valla et al., 1994) is a structured pictorial instrument assessing mental disorders in 6- to 11-year-old children. The Dominic assesses a child's perception of her/his own symptoms, which is critical to balance parents' and school professionals' perception. Ninety-nine drawings represent situations corresponding to DSM-III-R based ADHD, Conduct Disorder, Oppositional Defiant Disorder, Major Depressive Disorder, Separation Anxiety Disorder, Generalized Anxiety Disorder and Specific Phobia. The instrument takes 15-20 min to administer. The paper version of the Dominic questionnaire has been extensively validated (Valla et al. 1994, 1997b, 2000a). Intra-class correlation coefficients (ICCs) between test and retest ranged from 0.71 to 0.81 in a Montreal sample of 340 community children, and test-retest kappa values ranged from 0.44 to 0.69, with most kappa values around 0.60 (Valla et al. 1997b). Internalizing (53 items) and externalizing (42 items) disorder scales both yielded Cronbach's alphas of 0.89 (Cronbach 1951). Clinically referred (n=73) and non-referred (n=70) samples showed significant differences for every diagnosis ($p \leq 0.01$) using *t*-tests on mean scores. Kappa values ranged from 0.64 to 0.88 between *Dominic*-based diagnoses and DSM-III-R diagnoses based on clinical judgment in a sample of 117 general population children (Valla et al. 1994a).

Because of the lack of agreement between informants concerning the mental health of children, there is an obvious need to gather standardized information from children themselves on their own mental health.

By increasing young children's understanding of questions assessing mental health symptoms using a combination of visual and auditory signals, and by avoiding time-related components, the *Dominic-R* questionnaire allows reliable standardized assessment of children as young as 6 years. The DOMINIC-R is a structured, picture-based questionnaire (Valla, Bergeron, Berube, Gaudet, & St-George, 1994). With its original

format and robust psychometric properties, the *Dominic-R* questionnaire brings the structured interview of young child informants in line with standard clinical practice. The DOMINIC-R provides multiple symptom scales including attention deficit/hyperactivity disorder, conduct disorder, depression/dysthymia, overanxious disorder, oppositional defiant disorder, separation anxiety disorder and simple phobias.

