The *Dominic-R* is appropriate for both clinical and epidemiologic purposes with strong test - re-test reliability with younger children (i.e., 6 – 11 years of age; Valla et al., 1997). Instead of being organized in diagnostic modules, symptoms have been randomly mixed to avoid the halo effect, and normal situations are intermixed with DSM-III-R abnormal behaviours. The Dominic character may be interpreted either as a boy or a girl to allow assessment of both genders. The pictorial format is in keeping with best clinical practice and with the cognitive abilities of young children, and at the same time complies with the epidemiological requirement for standardized assessment by lay interviewers.

We will analyze the results for each subscale independently. We predict a significant effect for birth weight (corrected for gestational age) on scores for the attention deficit/hyperactivity disorder, depression/dysthymia, overanxious disorder, separation anxiety disorder and simple phobias, reflecting the known relations between fetal growth and emotional function in childhood. We will also provide preliminary analyses on the scales for conduct disorder and oppositional defiant disorder for which there is to date very little data linking prenatal development to outcomes. We also predict that the effects of fetal growth will be moderated by the quality of postnatal mother – child relation such that the statistical relation between birth weight and clinical outcome will be non-significant in children with a high quality of maternal care and with a secure level of attachment. This finding will be represented as a significant statistical interaction (see below).

NEPSY: A Developmental Neuropsychological Assessment (15 minutes)

The NEPSY consists of a series of neuropsychological subtests offering a comprehensive assessment of neuropsychological development in children 3-12 years of age. These subtests enable the examiner to evaluate and explore the deficiencies that interfere with the child's learning. Some subscales (Sensory motor functions, Visuospatial processing) of the NEPSY have been accepted by the ERB for the 48 month assessment. But for the 72 month visits, we will focus on the language domain including the following subtests: Verbal Fluency (speeded naming), repetition of pseudowords, phonological processes.

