The NEPSY is used as an age-appropriate measure for child general IQ for use as a potential covariate for effects on child emotional/cognitive functions.

Child Attribution Style Interview (24 items)

The Child Attributional Style Interview (CASI) is a measure of attributional style in children aged five years old and older. The interactive interview consists of sixteen events, which are presented to the child as 8 and ½” X 11” illustrations, in a storybook format. The events are centered on a main character; matched on gender to the child interviewed. The events are equally divided on two domains: valence (positive and

negative theme), and interpersonal (parents and peers) and achievement. This creates the possibility of four sub-categories for analysis (i.e. positive-achievement, negative-interpersonal etc.). After the presentation of each event, the child is asked three questions for their level of internal, stable and global attributions for each event. For example, to ask about how the child might internalize the cause of the event the research assistant asks the child, "How much is the event *because* of you?". To answer each question the child moves an arrow on a sliding scale, along an isosceles triangle. The larger side of the triangle represents in the example above, "*more because* of me" and the narrow side represents "*less because* of me". The CASI takes approximately 30 minutes to administer, which includes two practice sessions and administration of the sixteen CASI events.

The measure has been validated in a sample of five to seven year old by Conley, Haines, Hilt and Metalsky (2001) in a prospective, longitudinal study. The internal consistency for the measure was found to be between .73-.82 in children aged five and .77-.82 in children aged seven. In line with the reformulated learned helplessness theory, the children's answers on the CASI and self-esteem predicted changes in depression scores in times of increased stress. It should be noted that Conley et al. (2001) found that the younger children were more likely to pick extreme ends for each domain. However, the researchers found that the children had no bias for one extreme over another.

Seventy-two month interview: Laboratory visit (135 minutes)

Mother-child interaction (120 minutes)

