The inclusion of the CASI permits a direct measure of potential cognitive mechanisms for individual differences in the risk for psychopathology. The questionnaire measures the inclination for positive/negative self-attribution, which is considered linked to the risk for affective illness (Seligman et al., 1984). We will use the positive – negative subscale scores in a multivariate analysis. If indeed cognitive attributional style is a mediator for the vulnerability reflected in the DOMINIC-R scales, then the inclusion of this measure, especially the negative scale, should significantly reduce the predicted interaction effect between birth weight and child attachment.

Hypothesis 2: The quality of postnatal mother – infant interaction will be associated with differences in the quality of the maternal environment and maternal mental well-being. We will essentially use an analysis similar to that for case – control studies, splitting data according to child attachment category (secure vs insecure). We will use independent t-tests to compare the data for mothers of secure versus insecurely attached children on the McMaster Model of Family Functioning (MMFF) with separate analyses of the six subscales of the MMFF (Problem solving, communication, roles, affective responsiveness, affective involvement, behaviour control) as well as on the General Functioning scale that measures the overall level of the family’s functioning. We predict significant differences across all scales. Subsequent analyses will explore the possibility that one subscale may be a better predictor of child attachment.

References

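### CASI is tested as a mediator only against DOMINIC-R, and the same child answers both at the same visit, so shared reporting can be read as mediation (minor)

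*Protocol*

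**What the plan says.** All of this is in the Protocol for the 72-month extension.

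- **Same visit.** The heading that begins "Seventy-two month interview: Home visit (150 minutes" covers a mothers' part and a children's part. DOMINIC-R ("THE DOMINIC=R QUESTIONNAIRE: (20 minutes") and CASI are both in the children's part, before the laboratory visit starts.
- **Same informant.** DOMINIC-R records the child's "perception of her/his own symptoms". On CASI the child answers each question by moving an arrow along a triangle.
- **The mediation step.** Analyses, Hypothesis 1, says of CASI: "If indeed cognitive attributional style is a mediator for the vulnerability reflected in the DOMINIC-R scales", then adding it, especially its negative scale, should significantly reduce the birth weight x attachment interaction. The model is described only as multivariate. The step names no outcome from another informant, no test of the indirect effect and no allowance for answering style.
- **What is known of answering style.** The CASI description reports from the validation study that "younger children were more likely to pick extreme ends for each domain". Its next sentence adds that neither end was favoured.
- **Other informants.** The Strengths and Difficulties Questionnaire (SDQ) is in the mothers' part of the visit, described as "5 minutes) for screening psychopathology in children". No analysis uses it. Conners and BRIEF receive the interaction test, and Conners is to be correlated with the child's self-report, but neither is linked to CASI.

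**The concern.** Two self-reports from one six-year-old on one day can correlate for reasons other than attributional style acting on symptoms. A child who agrees readily, or is low that day, may score higher on both. The criterion is a drop in the interaction after CASI is added, and it cannot tell that correlation from a causal path. A formal indirect-effect test on the same two scores would have the same weakness.

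At stake is a reported cognitive mechanism that is partly a reporting artefact. The plan recognises informant differences elsewhere: it justifies DOMINIC-R by saying that "there is an obvious need to gather standardized information from children themselves on their own mental health", and it counts overlapping measures as a strength because they can converge. The CASI step is where that cross-check is not applied.

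**Working it through.** The plan gives no sample size, power or effect size for the CASI step, so there is no stated figure to reproduce. The calculation below shows when the problem arises and how large it could be.

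**Inputs from the Protocol.** About 600 children are enrolled. Only birth-weight percentiles 0-20, 21-40 and 41-70 are analysed. Analyses are stratified by gender.

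**Assumptions.** Percentiles are uniform, giving 600 x 0.70 = 420 children, class shares 2/7, 2/7, 3/7, and 420/2 = 210 per gender. Attachment is insecure in 35%. Birth-weight class is coded 0, 1/2, 1. The interaction on DOMINIC-R is 0.7 SD, and on CASI d = 0.7 or 0.5 SD. A shared style makes up a fraction s of the residual variance of both scores. CASI has no effect on symptoms.

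**Step 1, the false path.** Given birth weight and attachment, both scores have residual variance 1 and covariance s. The CASI slope for DOMINIC-R is therefore b = s, although the true slope is 0.

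**Step 2, the false drop.** The interaction falls by s x d, a share s x d/0.7. For s = 5, 10, 15, 25% the share is 5, 10, 15, 25% at d = 0.7, and 4, 7, 11, 18% at d = 0.5. At d = 0 it is zero whatever s is.

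**Step 3, how often both paths reach p < .05.**

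- Variance of class: (0.25 x 2/7 + 1 x 3/7) - (4/7)^2 = 0.5 - 0.3265 = 0.1735. Variance of attachment: 0.35 x 0.65 = 0.2275.
- SE of the interaction on CASI at n = 420: 1/sqrt(420 x 0.1735 x 0.2275) = 0.2456. For d = 0.7, z = 2.85 (power 81%). For d = 0.5, z = 2.04 (power 53%). At n = 210 the SE is 0.347 and the powers are 52% and 30%.
- CASI to DOMINIC-R path: z = s x sqrt(n)/sqrt(1 - s^2). At n = 420 this is 1.03, 2.06, 3.11, 5.29 for the four values of s, with power 18, 54, 87 and nearly 100%.
- The joint rate is close to the product of the two powers:

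| Shared variance s | n=420, d=0.7 | n=420, d=0.5 | n=210, d=0.7 | n=210, d=0.5 |
|---|---|---|---|---|
| 5% | 14% | 9% | 6% | 3% |
| 10% | 44% | 29% | 16% | 9% |
| 15% | 71% | 46% | 31% | 18% |
| 25% | 81% | 53% | 50% | 29% |

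Simulation of the same model agrees within about two percentage points, giving about 10-82% at 420 and 3-49% at 210.

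**Step 4, comparisons.** With an outcome that does not share the child's style, the slope path is significant only 5% of the time. At n = 420 the joint rate is then 0.05 x 81% = 4% or 0.05 x 53% = 3%; at n = 210 it is 0.05 x 52% = 3% or 0.05 x 30% = 2%. If CASI does not vary with birth weight x attachment, the rate is at most 5% and the mean drop is zero.

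**The case against.** Several objections stand.

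- **Extreme answering is not the mechanism.** A reader might infer from the CASI description that children who use the ends of the scale score high on both instruments. Because neither end was favoured, extremity widens the spread without raising the score. Simulating symmetric extremity gave 3-6% false mediation and a mean drop of about zero. The concern needs a directional tendency, such as readiness to agree or low mood, which the documents do not report for either instrument. They also do not exclude it: the no-favoured-end finding concerns the group on CASI, not differences between children across two instruments.
- **The figures depend on modelling choices.** If the positive and negative CASI subscales are combined as a difference, shared style cancels and the false rate is 1-3%. If they are entered jointly, it is 13, 37, 63 and 79% at d = 0.7 and n = 420. The plan does not say which. Joint significance is also a stand-in for the plan's own rule, a significant reduction in the interaction.
- **The bias is not all one way.** CASI's internal consistency of .73-.82 would weaken a true path.
- **The SDQ's absence is partly a matter of scope.** The Analyses section limits itself to new measures, and the SDQ was approved earlier. A reader might take its omission for an oversight, but the documents do not show that.

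What remains is that CASI is tried against one outcome only, reported by the same child on the same day.

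**Conclusion.** The point holds in a conditional form and is minor. Shared reporting can be read as mediation when CASI varies with birth weight x attachment. The plan expects that condition, since without it no systematic drop could appear. It would be too strong to say that shared style will be counted as mediation, or that the tabulated rates are expected error rates. Every effect size and every value of s is assumed, and the documents support none of them in particular. The per-gender columns are closer to the stated analysis than the 420 columns.

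The severity is minor because the CASI step is a conditional follow-on, not one of the two stated hypotheses. That mothers rate the SDQ is inferred from its heading.

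**What to change.** In Analyses, Hypothesis 1, add to the CASI paragraph:

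- Repeat the CASI step with the SDQ score from the same visit as outcome, and with Conners for attention symptoms. Report these beside the DOMINIC-R result.
- If the CASI path appears only in child self-report, describe mediation as provisional and state the limitation: same informant, same visit.

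The SDQ should not act as a veto. The plan collects child reports because informants disagree, and the SDQ is a short screen on which mothers may miss internal symptoms. A null SDQ result therefore does not disprove mediation.

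Any adjustment for answering style should be exploratory at most. The share of CASI answers at the scale ends measures symmetric extremity, not readiness to agree. An index from DOMINIC-R's normal pictures ("normal situations are intermixed with DSM-III-R abnormal behaviours") may have little to work with: of 99 drawings, 53 internalizing and 42 externalizing items leave 99 - 53 - 42 = 4 if the scales do not overlap.

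The cost is analysis wording and a few extra models. The measures are already planned for the 72-month assessment, so no new instrument is needed.

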Attachment protocol: The Strange situation. The primary purpose of this paradigm is to assess the establishment and quality of infant-mother attachment. This procedure has already been accepted the Douglas Hospital Ethic Board for the 18 and 36 month visits. At 72 month, we will use the procedure adopted by Main & Cassidy (1988) involving two long separations and two reunions. On arrival at the lab, mothers and children will ask to stay together in the Strange Situation room for 10 minutes (free play) followed by a separation (approximately 45 minutes) during which the child will complete problem-solving tasks with an experimenter while the mother complete questionnaires in another room. Just prior to the reunion, there will be a free-play session during which the experimenter was available to the child. Following the separation, mothers will be told to rejoin the child but will receive no specific instructions concerning the reunion. After the 5-minute reunion period, the mother and child remain in the room for a 10-minute snack time. A second 30-minute separation and 5-minute reunion period (structured like the first) will then take place. The child's attachment classification is given on the basis of behavior observed during both reunion periods. The predictive validity of this procedure for classifying attachment behavior in children of this age range with respect to socio-emotional and academic adaptation has been demonstrated in studies by Cassidy (1988), Cohn (1990), Easterbrooks, Davidson and Chazan (1993), Main et al. (1985), Moss et al. (1996; 1998), Moss and St-Laurent (2001), and Solomon et al. (1995). The scoring of this interaction is supervised by [name] at UQAM, a noted expertise in the area of child attachment. [name] is responsible for the

training of coders. The attachment classifications used in this study are secure versus insecure.

Mothers

Questionnaires (30 minutes)

The following questionnaires have already been accepted by the Douglas Hospital Ethic Board. The CEBQ (Child Eating Behaviour questionnaire examine eating behaviour and the Food Frequency questionnaire is a questionnaire on feeding patterns.

Sensitivity to Reward and Sensitivity to Punishment questionnaire (10 minutes)

This measure has already been accepted by the Douglas Hospital Ethic Board for the 60 month assessment. At 72 months, we will use the children version of this questionnaire.

BRIEF (Behavior Rating Inventory of Executive Function) (15 minutes)

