The observations of parents and teachers provide a wealth of information about a child's behavior that is directly relevant to an understanding of that child's executive functioning. The BRIEF-P is the first standardized rating scale designed to specifically measure the range of behavioral manifestations of executive function in preschool-aged children--thus facilitating intervention at earlier stages of development. The BRIEF-P consists of a single Rating Form used by parents, teachers, and day care providers to rate a child's executive functions within the context of his/her everyday environments--home and preschool. The original Behavior Rating Inventory of Executive Function™ (BRIEF™) was the basis for the development of the BRIEF-P. Consequently, the BRIEF-P is an ecologically valid and efficient tool for screening, assessing, and monitoring a young child's executive functioning and development.

Children

Attention Tests: CANTAB (60 minutes)

This measure has already been accepted by the Douglas Hospital Ethic Board for the 60 month assessment. For the 72 mo assessment, we will use the same subtests as used in the 60 month protocol. The CANTAB battery will be performed during the 2 separation periods of the Strange Situation. During this separation, the mothers will be asked to fill in questionnaires in a separate room.

Nutritional status: Body weight and body fat percentage will be measured using the Tanita® BF 625 scale (foot to foot bioelectrical impedance) which functions as a portable regular scale. Height will be measured using a stadiometer. These measures have already been accepted by the Douglas Hospital Ethic Board for the 48-month assessment.

Analyses

In accordance with CIHR policy on identifying gender effects, analyses will be stratified by gender. Statistical significance will be corrected for multiple comparisons where appropriate. The sample size (currently ~600 children are enrolled in the MAVAN study) is well above the range of published interaction studies [e.g., 3,4,7-9,11], which typically include 100-150 subjects. As per the comments on the previous submission, we focus on the analyses of the new measures. Please note that the MAVAN Project has been funded by CIHR (2009-2014; Behavioural Sciences B) to examine birth weight x genotype interaction effects on cognitive development using the CANTAB measures described here as well as the Connors Rating Scale ([name] (PI) and [name] (Co_PI)).

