Hypothesis 1: The relation between birth weight and measures of childhood mental health will be moderated by the quality of post-natal maternal care. We will focus on two outcomes measures, the Connors questionnaire and the DOMINIC-R questionnaire. We predict a significant interaction between birth weight corrected for gestational age x child attachment (secure versus insecure). Birth weight will be examined as a categorical variable using the following percentile groupings for birth weight for gestational age (0-20%, 21-40% and 41-70%). These percentiles are calculated using contemporary Canadian norms (Kramer, 2001). We have previously used these groupings to show significant effects of birth weight on tests of attention and impulse control. The results will be analyzed using a two way ANOVA (birth weight class) x attachment category, with a predicted interaction effect (post-hoc analyses) such that birth weight effects are apparent only amongst children showing insecure attachment. Subsequent ANCOVA's could be used to test the effects of possible moderators, including measures of sleep quality, which can affect mood as well as cognitive performance.

The same analysis will be applied to the results of the Connors Rating Scale, which is included as the current standard rating scale measure for symptoms associated with the Attentional Deficit Hyperactivity Disorder. The use of this measure also allows us to correlate a standard parent/teacher rating scale to the self-report measures of the child. Likewise, we predict a similar birth weight x child attachment interaction effect on the BRIEF (Behavior Rating Inventory of Executive Function) measure of executive function. A strength in this approach is that of the overlapping measures. While this implies greater number of statistical tests, this is the opportunity for the establishment of converging evidence should the predict interaction emerge in each of these analyses.

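### The CASI mediation analysis names no test or interval for the drop in the interaction, and same-visit child reports cannot show direction

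*Protocol*

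**What the plan says.** Under Hypothesis 1 in the Analyses section, the Protocol tests DOMINIC-R outcomes with a "two way ANOVA (birth weight class) x attachment category". Birth weight for gestational age is in three percentile classes ("0-20%, 21-40% and 41-70"). The Strange Situation paragraph says: "The attachment classifications used in this study are secure versus insecure".

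The CASI paragraph then presents attributional style as a possible cognitive mechanism and enters its positive and negative "subscale scores in a multivariate analysis", not specified further. The inference is conditional: "If indeed cognitive attributional style is a mediator for the vulnerability reflected in the DOMINIC-R scales", then including CASI, above all its negative scale, "should significantly reduce the predicted interaction effect between birth weight and child attachment". No statistic, interval, threshold or power is given for this step.

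Three other statements bear on it. The Analyses section says that "analyses will be stratified by gender" and promises a multiplicity correction where appropriate. The DOMINIC-R section treats each subscale as a separate analysis. The Measures section lists CASI and DOMINIC-R together among the child measures of the 72-month home visit.

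**The concern.** A covariate-adjusted ANOVA gives one F test for the interaction without CASI and another with it. Neither tests the difference between them, so whoever runs the analysis must decide what counts as a significant reduction. Three rules are open: the interaction loses significance, the coefficient gets smaller, or the change is formally tested. They can give very different answers on the same data.

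Direction is a separate problem. The CASI section supports the instrument with a prospective study in which CASI answers, with self-esteem, predicted later change in depression scores. The planned analysis has no such time order, because mediator and outcome come from the same child at the same visit. At stake is whether the study claims a cognitive mechanism. The primary interaction test is not affected.

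**Working it through.** The documents give no power or error rate for this analysis, so there is no stated figure to reproduce. The check is algebra plus simulation.

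**Inputs from the Protocol.** Three birth-weight classes by two attachment classes, so the interaction has (3 − 1) × (2 − 1) = 2 df; "currently ~600 children are enrolled in the MAVAN study"; gender strata.

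**Assumed inputs.** 70% of children fall in the three classes, giving 0.70 × 600 = 420, or 420 / 2 = 210 per gender. Class split 2/7 : 2/7 : 3/7; 40% insecure; SD 1; two-sided alpha 0.05 without multiplicity correction. There are seven true-mediation scenarios, with a3 (interaction to CASI) 0.5 to 1.2, b (CASI to DOMINIC-R) 0.3 to 0.5, and 30% to 100% of the interaction mediated. 1000 replicates each. CASI measurement error is not modelled.

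**Step 1: what the drop is.** Let c be the interaction coefficient without CASI and c′ the coefficient with it. In least squares on the same children, c − c′ = a3 × b. This held in every replicate for the linear birth-weight contrast. Example: a3 = 0.8, b = 0.4, c′ = 0.32 gives c = 0.32 + 0.8 × 0.4 = 0.64, so 0.32 / 0.64 = 50% is mediated. The drop is therefore the indirect effect. What the plan lacks is its uncertainty.

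**Step 2: how often true mediation is missed.** Ranges are over the seven scenarios. The formal test is a Sobel test of a3 × b.

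| N | Loss of significance, linear contrast | Loss of significance, 2-df F | Formal test of the change |
|---|---|---|---|
| 600 | 18–84% | 26–87% | 0–33% |
| 420 | 33–86% | 46–90% | 0–47% |
| 210 | 61–93% | 67–94% | 7–77% |

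When about half the interaction is mediated (total 0.64 to 0.80 SD), loss of significance misses 53–63% (linear) or 50–55% (F) at N = 600. At N = 210 the two such scenarios miss 61% and 70.5% (linear).

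**Step 3: where the misses come from.** Take the Step 1 example at N = 420 with the linear contrast. The interaction is significant before CASI in 77.1% of replicates, and significant before but not after in 46.8%. So 100 − 77.1 = 22.9% fail because there was no significant interaction to lose, and 77.1 − 46.8 = 30.3% fail because it stayed significant. The total missed is 53.2%. The formal test detects mediation in 90.7% of the same replicates.

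**Step 4: shrinkage without mediation.** If CASI is unrelated to the interaction, the mean change is −0.5% to 0.0%. The coefficient still falls in about half of samples by chance, so a raw drop is no criterion. If symptoms drive a standardised CASI with path k, then a3 = k × c and b = k, so c′ = c(1 − k²). The shrinkage is k²: 0.3² = 9% and 0.5² = 25%. Simulation at N = 600 gave:

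| No mediation | Mean shrinkage | Formal test signals mediation | Loss of significance (linear) does |
|---|---|---|---|
| Symptoms drive CASI, path 0.3 | 9% | 23% | 1% |
| Symptoms drive CASI, path 0.5 | 25% | 52% | 5% |
| Shared latent trait | 25% | 69% | 15% |

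**Step 5: interval and reverse-order model.** A separate simulation used a single interaction coefficient, n = 300 to 500, a3 = b = 0.4 and a direct effect of 0.16. Since 0.4 × 0.4 = 0.16, half is mediated. A 95% interval for the indirect effect detected mediation in 90–99%, against 44–48% for loss of significance. With symptoms driving CASI and no mediation, the interval falsely signalled it in 11–42%, against 3–16%. Under true forward mediation, the reverse-order interval also excluded zero in 69–90%, so it cannot tell the two directions apart.

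**The case against.** The strongest reply is that the Protocol never writes a loss-of-significance rule. A significant reduction can fairly be read as a test of the change, and by Step 1 that change is the indirect effect. This stands: a reader might infer that the plan tests nothing relevant, but it points at the right quantity and omits the test. The loss-of-significance reading remains plausible, because the DOMINIC-R section also reasons from a relation becoming non-significant in securely attached children, although it then calls for an interaction test.

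A second reply is that no miss rate belongs to the plan, since the documents give no effect sizes and no share insecure. This also stands. The rates show what depends on the choice of rule.

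A third is that the indirect-effect interval is itself open to reverse causation, and signals false mediation more often than loss of significance does. Steps 4 and 5 confirm this. It limits what the interval can be used to claim, but does not make an unspecified reduction preferable.

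Finally, the analysis is secondary and conditionally worded, and section IV of the Combined protocol and SAP already lists direct and indirect effects under structural equation modelling. But that 2004 plan does not include CASI, and the CASI paragraph does not call on it.

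**Conclusion.** The point holds as a gap in specification and a limit on interpretation. The plan infers mediation from a reduction for which it names no test or interval. If loss of significance is the rule used, misses run from 18% to 94% over the scenarios and sample sizes examined. They are about half at N = 600 when half the interaction is mediated, and higher within a gender stratum. These figures rest on the assumed effects, class split, share insecure and alpha listed above.

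Two stronger readings are not supported. One is that the interaction shrinks without mediation as a general matter: its expected change is zero when CASI is unrelated to the interaction, and shrinkage needs reverse causation or a common cause. The other is that an interval for the indirect effect would establish the mechanism: it improves detection, but with both measures taken at one visit it cannot establish direction. The change is worth making because it decides whether a cognitive mechanism is claimed; the primary test of Hypothesis 1 does not depend on it.

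**What to change.** Replace the reduction criterion with a named mediated-moderation model. On the children with both measures, estimate the indirect interaction: the effect of birth weight by attachment on the CASI negative score, times the effect of CASI on the DOMINIC-R scale. Use a linear birth-weight contrast, or both contrasts of the three-class factor, and give a bootstrap 95% confidence interval. State how the planned multiplicity correction applies across DOMINIC-R scales and gender strata; seven scales by two genders is 7 × 2 = 14 analyses.

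Treat an interval that excludes zero as necessary, not sufficient. Report the result as a cross-sectional association consistent with mediation, and say that symptoms shaping attributions or a shared cause could produce it. A reverse-order model may be shown beside it, with a note that it cannot settle direction.

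No new data are needed. The cost is a little more analysis work and a more guarded mechanism claim.
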